# 2.7.2. Secondary Endpoints

Secondary endpoints will be analyzed for between- and within-group differences using ITT, PP (per protocol) and AT (as treated) analyses (see sections 2.7.1 and 5.2.)(Figure 2).

The *PP population* will be defined as the following:

In the arthroscopy group, included patients are: All patients randomized to arthroscopy that went through surgery, and not have had postoperative active physiotherapy (exercises) more than 80 % of twice a week in 12 weeks (19 or more sessions)(equivalent to 80 % in the exercise group), are included.

In the exercise group patients who participated in the program with at least 80 % compliance during the 12 weeks intervention period and did not cross over to the surgical treatment arm during the 2 years period and not have had any other surgery to the index knee (osteotomy, arthroplasty) within two years, are included.

This means that the following will be excluded from the PP analysis:

- 1) Those who were randomized to arthroscopy
  - a. but never went through surgery
  - b. but had postoperative exercise therapy supervised by physiotherapists (defined as 19 or more sessions )
- 2) Those who were randomized to exercise therapy supervised by physiotherapist
  - a. but never went through exercise or participated in less than 19 sessions ( 80 % of the minimum of 24 exercise sessions)
  - b. but crossed over to the surgical treatment arm within 2 years

The AT population will be defined as the following:

In the arthroscopy group, included patients are: All patients randomized to arthroscopy that went through surgery, and not have had postoperative active physiotherapy (exercises) more than 80 % of twice a week in 12 weeks (19 or more sessions)(equivalent to 80 % in the exercise group), are included. Additionally; Patients from the exercise group that within 2 years crossed over to surgery, are included in the arthroscopy group.

In the exercise group patients who participated in the program with at least 80 % compliance

during the 12 weeks intervention period and did not cross over to the surgical treatment arm during the 2 years period and not have had any other surgery to the index knee (osteotomy, arthroplasty) within two years, are included. Additionally; patients from the arthroscopy group that within two years crossed over to exercise (performed more than 80 % of twice a week in 12 weeks (19 or more sessions), are included in the exercise group.

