## 4. Study Population

#### 4.1. Subject Disposition

Study procedures, including recruitment strategies and inclusion and exclusion criteria, have been described in the PhD protocol (Appendix 1). Patients included in the trial were randomized to: A) Exercise therapy or B) Arthroscopic partial meniscal resection. All consecutive patients who came to the two inclusion sites on the days of the orthopedic surgeons outpatient clinic fulfilling the eligibility criteria were asked to enter the study. Patients fulfilling all eligibility criteria, but refusing to participate in the randomization, were registered.

Crossovers are a common problem in studies randomizing to surgical or non-surgical treatments. In this study participants who experienced impairment of their symptoms or lack of improvement during the 2-year observation period, were reassessed at any time when necessary by the orthopedic surgeon who was responsible for the study. Indication for surgery (crossing over from exercise to arthroscopy) or re-operation (meniscal re-resection or other surgery in the index knee within 2 years) was based upon patient's history, clinical and radiological examinations.

Patients from the arthroscopy group that had postoperative active exercise therapy supervised by a physiotherapist more than 80 % of twice a week in 12 weeks (19 or more sessions)(equivalent to 80 % in the exercise group) were regarded as crossing over to the exercise group.

The frequency of crossovers from exercise to arthroscopy and vice versa, re-operations with meniscal re-resections or other surgery in the index knee within 2 years will be registered and reported (Table 3).

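### The PP and AT definitions make other index-knee surgery a condition for the exercise group only, the PP exclusion list omits it, and AT leaves some exercise patients unplaced

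*SAP*

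**What the plan says.** Section 2.7.2 sets the scope: "Secondary endpoints will be analyzed for between- and within-group differences using ITT, PP (per protocol) and AT (as treated) analyses". It then defines the two populations arm by arm.

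- **Exercise, PP and AT.** The patient must have at least 80% compliance, must not have crossed over, and must "not have had any other surgery to the index knee (osteotomy, arthroplasty) within two years, are included".
- **Arthroscopy, PP and AT.** The group is "All patients randomized to arthroscopy that went through surgery, and not have had postoperative active physiotherapy (exercises" at a level of 19 or more sessions. Later surgery on the same knee is not mentioned.
- **AT additions.** On one side, "Patients from the exercise group that within 2 years crossed over to surgery, are included in the arthroscopy group". On the other, "patients from the arthroscopy group that within two years crossed over to exercise" join the exercise group, on the session count alone.
- **PP exclusion list.** It is introduced as a restatement of the PP definitions. Its last exercise item is "but crossed over to the surgical treatment arm within 2 years". Osteotomy and arthroplasty do not appear.

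Section 4.1 describes how further surgery comes about: "participants who experienced impairment of their symptoms or lack of improvement during the 2-year observation period, were reassessed" by the responsible surgeon, who judged the indication for crossover or re-operation. It also says that "re-operations with meniscal re-resections or other surgery in the index knee within 2 years will be registered and reported". Table 3 has a row for other index-knee surgery in the arthroscopy group. For the exercise group, that row appears only under re-operations after crossing over.

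**The concern.** Other index-knee surgery happens after randomization and, by the SAP's own account, follows a poor course. If it removes patients from one arm while their counterparts stay in the other, the comparison is no longer like with like. The PP or AT contrast can then move without any treatment effect.

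There is also a plain problem of specification. Section 7 makes the SAP the statistician's work description. On this point it gives two answers for PP and, for some patients, none for AT. Someone would have to choose after data collection. At stake are the PP and AT results for secondary outcomes, which readers will use to judge whether crossover hides a difference.

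**Working it through.** No figure in the plan quantifies this point, so there is none to reproduce. The check is mainly a comparison of texts.

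**Step 1. Follow one type of patient through each text of section 2.7.2.** The patient has osteotomy or arthroplasty of the index knee within 2 years, and otherwise meets the conditions of the group named.

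| Patient | PP inclusion text | PP exclusion list | AT |
|---|---|---|---|
| Exercise, 19 or more sessions, no crossover | Out | Not excluded | Fails the exercise condition; no text places the patient in arthroscopy |
| Arthroscopy, had surgery, fewer than 19 sessions | In | Not excluded | In the arthroscopy group |
| Arthroscopy, had surgery, 19 or more sessions | Out (sessions) | Excluded (sessions) | In the exercise group, with no surgery condition |

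Three results follow:
1. The condition is one-sided in PP and AT.
2. The PP inclusion text and exclusion list disagree on the first row.
3. The AT exercise group applies the condition to patients randomized to exercise but not to those who join it from arthroscopy.

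**Step 2. Does crossover already cover the first row?** Section 4.1 explains crossing over as going from exercise to arthroscopy. On that meaning, osteotomy or arthroplasty without arthroscopy is not crossover, and the last item of the list does not reach it.

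**Step 3. Direction and size.** Let a share f of the otherwise eligible exercise group have such surgery, and let their mean change be d points lower than that of the rest, whose mean is m. Keeping everyone gives a mean of m − f × d; dropping them gives m. The shift in favour of exercise is therefore f × d. If d is negative, the shift reverses.

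Inputs: 140 randomized (section 1), so about 70 per arm, assuming equal arms. The SAP gives neither f nor d, so both are assumed.

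- 1 of 70: f = 1/70 = 0.0143; with d = 10, 0.0143 × 10 = 0.14 points.
- 2 of 70: f = 2/70 = 0.0286; with d = 20, 0.0286 × 20 = 0.57 points.

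The range is about 0.1 to 0.6 points. The PP group will be smaller than 70. With 48, the number per group in section 3.1 before dropout, the same counts give 1/48 × 10 = 0.21 to 2/48 × 20 = 0.83 points. As an upper illustration, f = 10% (7 of 70) with d = 10 to 20 gives 1.0 to 2.0 points, but nothing in the SAP suggests a share that high.

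**Step 4. What a rule for both arms achieves.** Write E for exercise and A for arthroscopy. If the criterion is dropped, this source of shift is zero. If it is added to both arms, the shift is f_E × d_E − f_A × d_A, which is zero only when the two products are equal.

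**The case against.** The best defence is that exercise is the non-surgical strategy, so any operation on the index knee departs from it, whereas further surgery is less plainly a departure in an arm allocated to surgery. That is a fair reason for a one-sided rule, but the SAP does not give it. It also does not reconcile the inclusion text with the exclusion list, and does not explain why arthroscopy patients who join the AT exercise group are exempt.

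A second defence is that AT may mean to count any index-knee surgery as crossing over to surgery, so these patients would be moved and not lost. The wording allows that reading, but section 4.1 points the other way. Figure 2, which section 2.7.2 cites for these groups, is not shown in the text at hand and may settle it. At the least, the text is ambiguous.

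Three limits stand in full:
- The criterion affects only compliant exercise patients who did not cross over and still had osteotomy or arthroplasty within 2 years. In patients aged 35 to 60 with Kellgren-Lawrence grade 0 to 2, these may be very few.
- Section 4.1 links re-operation to symptoms beforehand; the SAP says nothing about scores afterwards.
- The arthroscopy group also loses patients on a post-randomization criterion, the session count, so the net direction of all PP and AT exclusions together is unknown.

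**Conclusion.** The point holds as a defect of definition in secondary analyses. The one-sided condition and the PP contradiction can be read directly from section 2.7.2. The AT gap follows from section 2.7.2 with section 4.1's meaning of crossover.

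The numerical effect is unknown and probably small: about 0.1 to 0.6 points, assuming 1 or 2 of 70 patients removed and a deficit of 10 to 20 points.

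A reader might infer more than the document supports:
- **PP and AT are biased towards exercise whatever the true effect.** This needs the removed patients to score worse at 2 years, which is plausible but not stated.
- **Treatment failures leave one arm only.** That describes this single criterion, not the populations as a whole.
- **The shift is a sizeable part of the confidence interval.** The only SD given, 15, is for the primary outcome KOOS4. PP and AT concern secondary outcomes in smaller sets, so the SAP offers no suitable yardstick.
- **The main result is at risk.** It is not: the primary analysis is ITT on all randomized patients.

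**What to change.** Before unblinding:
1. Settle one rule for other index-knee surgery and apply it alike to both arms in PP and AT, including patients who change group in AT. Either drop the criterion from the exercise group or add it to both groups. Dropping it avoids selecting on this event at all. Adding it to both removes the one-sidedness, but the selection cancels only if rates and score deficits are alike.
2. Make the PP inclusion text and exclusion list identical.
3. State where AT places an exercise patient with such surgery and no crossover.
4. Report the number affected per arm, and add a Table 3 row for exercise patients with other index-knee surgery without crossover.

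The cost is slight wording and table work, and possibly a few patients more or fewer in PP and AT. No new data should be needed, since section 2.4 already has additional surgeries registered in both groups.

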## 2.2. Secondary Objectives and Outcomes

The secondary objectives are to compare change from baseline to the 2 years follow-up (including all follow-ups) between groups in a range of outcomes, except for isokinetic muscle strength and functional performance, for those the endpoint is 1-year follow-up.

Secondary outcomes differ from exploratory outcomes, because secondary outcomes will possibly enable clinical interpretations; not only be explanatory or hypothesis generating. Secondary outcomes give support to the primary outcome and will contribute to better interpretation and eventually more knowledge. Since secondary outcomes only are seen as supportive for the primary outcome, multiplicity is not considered to be a problem and not statistically corrected for.

These outcomes are:

1) The five subscales of KOOS in hierarchic sequence: a. QOL b. Sport/Rec. c. Pain d. Symptoms e. ADL.

2) Functional performance: a. The one-leg hop test b. The 6 meter timed hop test c. The kneebending test

3) Isokinetic muscle strength: a. Quadriceps strength b. Hamstrings strength

4) SF-36: Physical component summary (PCS) and mental component summary (MCS)

5) Global knee rating (much better – better– unchanged – worse – much worse)

7) To analyze the number needed to treat (NNT), based on a 15% difference in change in KOOS between groups from baseline to the 2 years applied in recent studies in similar patient populations, (see section 2.7.1.).

8) The health economic utility instruments EQ-5D index including EQ-5D VAS is included in the baseline and follow-up surveys. This will not be a part of this 2-year follow-up, but will be published later in a separate paper (see section 2.5.).

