## 5.2. Secondary Endpoints

Secondary outcomes are between- and within-groups comparisons of the change from baseline to the 2-year follow-up in all secondary endpoints except for the isokinetic muscle strength and functional performance data, where 1-year follow-up is the end point.

All outcomes will be checked for normality and statistical methods will be dependent on data distribution. When fulfilling the requirements for regression analyses, ANOVA analyses of the ITT populations will be conducted; otherwise non-parametrical tests will be used.

Finally, PP- and AT-analyses will be conducted in a range of secondary outcomes.

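### The per-protocol and as-treated sets use a 2-year crossover window even for endpoints that end at 1 year, so some 1-year results are classified by treatment received after they were measured

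*SAP*

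**What the plan says.** SAP section 2.7.2 sets the scope: "Secondary endpoints will be analyzed for between- and within-group differences using ITT, PP (per protocol) and AT (as treated) analyses". It then defines one PP set and one AT set, with no version by visit.

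- **AT, arthroscopy side:** "Patients from the exercise group that within 2 years crossed over to surgery, are included in the arthroscopy group".
- **AT, exercise side:** the set also takes in "patients from the arthroscopy group that within two years crossed over to exercise", meaning those who completed 19 or more sessions.
- **PP, exercise side:** patients are excluded if they were randomized to exercise "but crossed over to the surgical treatment arm within 2 years". Other index-knee surgery is ruled out over the same two years.
- **PP, arthroscopy side:** patients with 19 or more postoperative supervised sessions are excluded, with no stated time limit.

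Some secondary endpoints stop earlier. Section 2.2 plans change to 2 years "except for isokinetic muscle strength and functional performance, for those the endpoint is 1-year follow-up", and section 5.2 repeats this: "except for the isokinetic muscle strength and functional performance data, where 1-year follow-up is the end point". Section 2 explains why: the 2-year follow-up was a postal survey without these tests. Table 4 also labels global knee rating, VAS, BMI and self-efficacy as 1-year results.

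On how crossover arises, section 4.1 says that "participants who experienced impairment of their symptoms or lack of improvement during the 2-year observation period, were reassessed at any time when necessary". Table 3 has a row for crossover between 1 and 2 years in each direction.

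**The concern.** Membership of an analysis set should not depend on something that happens after the outcome is measured. Take an exercise patient operated on at month 18. The 12-month hop test was done after exercise only. The AT rule nevertheless counts it as an arthroscopy result, and the PP rule deletes it. An arthroscopy patient who reaches 19 sessions in year 2 is handled in mirror image: moved to exercise in AT, removed in PP.

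The later event is also unlikely to be unrelated to the earlier result. Patients were reassessed for surgery because they had worsened or failed to improve. Sorting 1-year data by surgery in year 2 can therefore take patients with poor 1-year results out of the exercise group and, in AT, place them in the arthroscopy group. The 1-year PP and AT results would then not compare the treatments patients had received by 1 year, although that is how readers will understand them.

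**Working it through.** The SAP gives no crossover rate and no figure for how later crossovers differ at 1 year. There is no planned figure to reproduce on this point, and the size has to be illustrated under assumptions.

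**Step 1: do the windows clash?** The sets look 24 months ahead (section 2.7.2). Strength and performance end at 12 months (sections 2.2 and 5.2) and are not measured at 24 months (section 2). Any PP or AT analysis of them on these sets therefore uses up to 12 months of later information. Table 3 shows that the plan allows for crossover in that interval.

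**Step 2: bias from exercise-to-surgery crossover alone.** Inputs:
- 140 randomized (section 1), taken as about 70 per arm (assumption).
- No true difference at 1 year: both arms, as randomized, have mean 0 (assumption).
- c = share of the exercise arm operated on after the 12-month visit (assumption).
- D = their deficit at that visit against exercise patients not operated on later (assumption). It is expressed in SD units because the SAP's SD of 15 belongs to KOOS4, not to strength or hop tests.

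With the exercise arm centred at 0, those not operated on later average cD and those operated on later average −(1−c)D.
- PP: exercise keeps only the first group, so the difference is cD − 0 = **cD**.
- AT: the arthroscopy mean becomes −c(1−c)D/(1+c), so the difference is cD + c(1−c)D/(1+c) = **2cD/(1+c)**.

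| Later crossovers of 70 | c | D | PP bias | AT bias |
|---|---|---|---|---|
| 0 | 0 | 1 SD | 0 | 0 |
| 5 | 0.071 | 1 SD | 0.07 SD | 0.143/1.071 = 0.13 SD |
| 10 | 0.143 | 1 SD | 0.14 SD | 0.286/1.143 = 0.25 SD |

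The bias is proportional to D, so a deficit of half an SD halves these values.

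**Step 3: effect on the test.** A simulation with 70 per arm and 20,000 runs, with c = 10% (7 patients) and D = 1 SD, rejected at a nominal two-sided 5% in 8.6% of runs for PP and 18.4% for AT. The comparison as randomized rejected in 4.2%. Over c = 5% to 20% and D from one third of an SD to 1 SD, the rates ran from about 5% to 21% (PP) and 6% to 51% (AT).

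**Step 4: add the reverse crossover.** Let a share r of the arthroscopy arm reach 19 sessions after the visit, with deficit E. Removing them raises the PP arthroscopy mean by rE, so the net PP bias is cD − rE. With c = 5/70, r = 10/70 and D = E = 1 SD, this is 0.07 − 0.14 = −0.07 SD, now favouring arthroscopy. With equal shares and deficits it is zero, and by symmetry the AT bias is zero too. The SAP does not say why arthroscopy patients took up exercise, so even the sign of E is open.

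**The case against.** **Scope.** Section 5.2 limits PP and AT to some secondary outcomes and otherwise describes secondary comparisons as change to 2 years, for which a 2-year window looks ahead to nothing. This stands for the 2-year endpoints. It does not clear the 1-year ones: section 5.2 names no outcomes and exempts none, and section 2.7.2 applies the sets to secondary endpoints generally.

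**Earlier visits.** A reader might infer that the 3-month results and the whole KOOS subscale curves are affected, since section 2.2 mentions all follow-ups. The text does not support this. No section states a PP or AT analysis at 3 months. Section 2.7.2 tests the subscales for change to 2 years and otherwise only plots them, without naming an analysis set.

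**Direction.** A reader might conclude that the rule favours exercise overall. That follows for exercise-to-surgery crossover taken alone, but Table 3 provides for crossover both ways and the net sign cannot be known from the SAP.

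**Size.** The figures rest on assumed values, and nothing shows that patients operated on later for symptoms were 1 SD worse on strength or hop tests a year or so earlier. The 70 per arm also ignores exclusions for fewer than 19 sessions. The 64 operations in section 3.2 are no better base, because the SAP does not say whether crossover operations are among them. All of this stands, so the figures are illustrations only.

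**Weight.** These analyses are supportive, secondary endpoints also get an intention-to-treat analysis, and PP and AT comparisons stay confounded by crossover before the visit whatever window is used. This stands too, but it does not justify adding a further bias that is easy to avoid.

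**Conclusion.** The point holds for the 1-year endpoints. Followed as written, the SAP classifies 1-year strength and performance results, and any other 1-year secondary outcome given a PP or AT analysis, partly by treatment received afterwards. This is a stated rule that gives a wrong classification, not a missing detail.

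Under the assumptions above (no true effect, about 70 per arm, a 1 SD deficit, 5 to 10 exercise patients operated on in year 2, no reverse crossover), the spurious difference toward exercise is about 0.07 to 0.14 SD in PP and 0.13 to 0.25 SD in AT. It is zero if nobody crosses over in year 2, and could have either sign once reverse crossover is counted. The primary KOOS4 analysis is by intention to treat and is untouched, so this should be corrected but does not threaten the main result.

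**What to change.** In section 2.7.2, define PP and AT status for every 1-year endpoint by surgery, or 19 or more supervised sessions, received before the 12-month visit. Keep the 2-year window for 2-year endpoints only. In section 5.2, name the outcomes that receive PP and AT analyses. If PP or AT results are shown at 3 or 12 months for other outcomes, for example in the KOOS subscale curves, apply the same rule of treatment received before that visit.

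The SAP already reasons this way for adverse events: in exercise patients who later have surgery, section 2.7.2 assigns treatment-dependent events before the operation to exercise and those during or after it to surgery. Crossover timing is already tabulated in Table 3, although in bands, so dates should be compared with the actual visit date.

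The cost is a few lines of SAP text and one derived status variable per visit. Set sizes will differ between visits and must be shown in Figure 2. The change removes the use of later information; it does not remove confounding from crossover before the visit, and the report should say so.

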## 2.4. Descriptive Assessments

Baseline characteristics will be presented in a table (Table 2).

Furthermore, the following treatment-related variables will be presented descriptively:

- Compliance with exercise during the 12 weeks is recorded from the patients exercise diary notes. The patients were instructed to complete two to three exercise sessions a week over twelve weeks (24-36 sessions). Compliance is assessed as the total number of exercise sessions completed out of the minimum of 24 sessions. *Excellent compliance* is defined as participation in 24 or more sessions (more than 100 %), *satisfactory compliance* is defined as 19-23 sessions (80-100 %) and *poor compliance* is defined as 18 or less sessions (less than 80 %). Less than 80 % compliance is defined as not completed treatment allocation.
- 2) Pain level during the 12 weeks exercise treatment is recorded from the patients exercise diary notes where they have reported pain on a visual analogue scale (VAS) during and after each training session.
- Satisfaction with the treatment effect will be registered at each follow-up until 12 months on a five-point Likert scale (very dissatisfied, dissatisfied, neither satisfied nor dissatisfied, satisfied, very satisfied).
- 4) Patients crossing over from the exercise group to arthroscopy and patients in both groups going through additional surgeries during the 24 months follow-up period will be registered (Table 3).
- 5) Patients crossing over from the arthroscopy group to exercise, not have had postoperative active physiotherapy (exercises) more than 80 % of twice a week in 12 weeks (19 or more sessions)(equivalent to 80 % in the exercise group).
- 6) Adverse events (AE) and seriously adverse events (SAE) will be registered and categorized into index knee or sites other than index knee. The project workers will record any adverse events that the participant experiences or tells them about and at all follow-ups all participants are asked about potential adverse events. For all participants in both groups including all patients crossing over (see section 2.7.1.) to the other intervention a project worker will look through hospital records to register if any pre-defined perioperative or postoperative adverse events occurred, or adverse events related to the exercise therapy (Table 1).

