The KOOS subscales Pain, Symptoms, ADL, Sport/Rec and QOL, EQ- 5D Index, EQ-5 VAS, weight and global knee function will be presented as mean (with 95% CI) for each treatment group. Between-group differences in change from baseline to 2 years will be statistically assessed. Each subscale of the KOOS will be presented graphically for its development over the 2 years period.

All issues during the trial found in the treatment records from the project physiotherapist, hospital records or the questionnaire from the follow-ups will be assessed to determine whether it represents an AE or not. AE will be presented in a table (see Table 1) and analyzed statistically by comparing actual numbers of serious AE (site other than index knee, index knee and all serious events) and non-serious AE (site other than index knee, index knee and all serious events).

AE associated with surgery will be given in Table 1 for the following groups:

1. Those receiving arthroscopic meniscal resection by randomization

2. All treatment dependent AE reported during and after surgery in those who had surgery even though randomized to the exercise therapy throughout the follow up period

AE associated with exercise therapy will be given in Table 1 for the following groups:

1. Those remaining in the 'Exercise therapy' group throughout the follow up period

2. All treatment dependent AE reported prior to the surgery in those who had surgery even though randomized to the exercise therapy

3. Those randomized to surgery but crossing over to exercise during the follow-up period

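### Between-group p-values for adverse events rest on counts pooled from sources that do not cover both groups equally

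*SAP*

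**What the plan says.** Section 2.7.2 takes as possible adverse events all issues "found in the treatment records from the project physiotherapist, hospital records or the questionnaire from the follow-ups". Each issue is judged to be an adverse event or not. The events are then "analyzed statistically by comparing actual numbers of serious AE", and likewise for non-serious events. The Table 1 shell has one column per treatment and a column for p-values. The SAP names no test, no denominator and no field for the source of an event.

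Section 2.4, item 6, describes collection: "The project workers will record any adverse events that the participant experiences or tells them about". Besides this, every participant is questioned on the matter at each follow-up. The hospital-record search applies to everyone, crossovers included: "a project worker will look through hospital records to register if any pre-defined perioperative or postoperative adverse events occurred". The same sentence adds events related to exercise therapy as a search target.

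Two other places show who is seen by whom. Section 2.4, item 1, prescribes 24 to 36 exercise sessions over twelve weeks. Section 3.2 says that exercise was given by one dedicated physiotherapist at each of two institutes, and that arthroscopy patients were treated at the hospital that recruited them.

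**The concern.** A between-group test of event counts compares harm only if an event has the same chance of being found in either group. Here one of three sources belongs to the delivery of one treatment. A transient knee complaint can be noted at one of 24 to 36 supervised sessions, yet be missed when the patient is next asked at 3, 12 or 24 months. The expected counts then differ even when true harm is equal, and a larger sample makes that difference more certain.

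Section 2.1 already notes that exercise patients had frequent contact with the physiotherapist, and it worries that treatment context affects KOOS scores. It does not carry that thought over to adverse events. What is at stake is how the safety comparison of surgery and exercise is read; the primary endpoint is not affected.

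**Working it through.** **Coverage of each source**

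| Source | Exercise group | Arthroscopy group | Basis |
|---|---|---|---|
| Project physiotherapist's records | 24–36 sessions | In effect none, except perhaps patients who crossed over to exercise | Inferred from 2.4 item 1 and 3.2 |
| Questions at follow-ups | All asked | All asked | Stated, 2.4 item 6 |
| Hospital-record review | All searched | All searched | Stated, 2.4 item 6 |

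The hospital review covers everyone, but only its peri- and postoperative targets are called pre-defined. It may therefore find more in operated patients.

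**Plan's own figure.** There is none for adverse events. The only calculation in the SAP (Section 3.1: 47.25 / 0.85 = 55.6, so 56 per group) concerns KOOS4 and has no bearing here.

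**Inputs for an illustration.** From the SAP: 140 randomised, taken as 70 per group. Assumed: one yes/no outcome per patient, the same true risk r in both groups, and a two-sided Fisher exact test at 0.05. Rejection rates come from exact enumeration of two binomials.

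**Model A: overall detection d_E (exercise) and d_A (arthroscopy).** Observed risks are r × d_E and r × d_A.

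| True risk | Detection | Observed | Rejection |
|---|---|---|---|
| 30% | 90% v 90% | 27% v 27% | 3.1% |
| 30% | 90% v 80% | 27% v 24% | 4.5% |
| 30% | 90% v 60% | 27% v 18% | 19% |
| 50% | 90% v 80% | 45% v 40% | 6.5% |
| 50% | 90% v 60% | 45% v 30% | 38% |
| 10% | 90% v 60% | 9% v 6% | 5.0% |
| 5% | 90% v 60% | 4.5% v 3% | 1.6% |

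A wider gap of 90% v 45% gives 44% at 30% risk and 77% at 50% risk.

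**Model B: the sources as the SAP describes them.** The shared sources detect a share s in both groups. The physiotherapist records find a share q of what those miss, in the exercise group only. Observed risks are r × s (arthroscopy) and r × [s + (1 − s) × q] (exercise). At r = 30%:

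- s = 0.9, q = 0.5: 27% v 0.30 × 0.95 = 28.5%; rejection 3.5%.
- s = 0.7, q = 0.5: 21% v 0.30 × 0.85 = 25.5%; rejection 6.5%.
- s = 0.5, q = 0.8: 15% v 0.30 × 0.90 = 27%; rejection 34%.
- q = 0 (shared sources only): rejection 3.0–3.1%.

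Both models run from about nominal to several times nominal. The result depends on the detection gap and on how common the event is. Within model B, dropping the extra source removes the distortion. Neither model includes better detection in operated patients, which would pull the other way.

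**The case against.** Several points weaken the concern. Two of the three sources cover everyone, and the hospital search includes exercise-related events. Section 2.7.2 does not count issues automatically, since each is first assessed. Session pain has its own place (diary scores, reported in Table 3). Arthroscopy patients were not reached by questionnaire alone: follow-up tests took place at one centre (Section 3.2), and patients who worsened or failed to improve could be reassessed by the surgeon at any time (Section 4.1). Adverse events appear under descriptive assessments in 2.4 and are not among the numbered secondary outcomes in 2.2, so no decision rule hangs on these p-values. The detection rates above are all assumed. The Table 1 columns are also formed partly by treatment received, so they are not 70 v 70 randomised groups.

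Most of this limits the size of the problem and leaves the problem itself in place. Assessment of each issue does not supply the events that were never noted in the group seen less often. Tabulating diary pain separately does not keep other complaints in the physiotherapist's records out of the tested counts.

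A reader might go further and infer that the p-values measure only how often patients were seen, or that exercise must come out looking worse. The SAP supports neither. The shared sources mean that the counts still carry information on harm, and the perioperative search may act in the opposite direction. Nor does the SAP tie the open-ended recording by project workers to the exercise sessions; that sentence refers to participants in general.

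**Conclusion.** The point holds in a limited form. Adverse-event counts are given between-group p-values although one pooled source in effect covers only exercising patients, and nothing in the SAP separates the sources or warns of the difference. The p-values therefore mix harm with detection.

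The effect should matter mainly for common, non-serious events. Serious events are more likely to reach hospital records or the follow-up questions in either group, and at true risks of 10% or below with 90% v 60% detection the illustrated rejection rate is about 5% or less. For common events it runs from 4.5% (30% risk, 90% v 80%) to 19–38% (30–50% risk, 90% v 60%).

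These figures rest on equal true risk, a per-patient Fisher test and detection rates that the SAP does not give. They show what is possible and do not estimate the bias in this trial. The exercise-only nature of the physiotherapist records is also an inference: the SAP does not say whether the project physiotherapist saw any arthroscopy patients who crossed over to exercise.

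**What to change.** In Section 2.7.2 and Table 1:

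- Base the between-group test on events found by the follow-up questions or the hospital-record review, the sources applied to all participants.
- At the assessment of each issue, which the plan already requires, record every source in which the event was found. An event seen in both physiotherapist records and a shared source stays in the test.
- Report events found only in physiotherapist records, and procedure-specific events, in a separate descriptive panel by source without p-values.

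The cost is SAP wording, one flag per event and one extra panel, and fewer events enter the test. No new data are needed, provided that the source can still be read from the records. A flag for physiotherapist records would reveal the group to the blinded statistician, so data for that panel should be released after the written blinded interpretation described in Section 3.2. The change does not settle how Table 1 assigns crossovers to columns, which needs separate attention.
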